3.2. Stratification, Randomization, and Blinding/Masking

This is a randomized, double-blind, placebo controlled study. After informed consent is obtained, eligibility information will be relayed to an unblinded laboratory staff member who will serve as the unblinded pharmacist. This staff member will then randomize subjects in a 2:1 allocation ratio (AMT cream: placebo). This unblinded pharmacist will use an online tool to generate a simple randomization list: <http://www.randomization.com/>. This lab member will notify the clinical team once participant has been randomized and is responsible for securely storing all randomization files.

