3.1. Description of Study Design

This is a single site, double blind placebo controlled study, which will assess the efficacy, safety, and steady state of Autologous Microbiome Transplant (AMT) cream in adults with AD. After providing informed consent, patients will be assessed for study eligibility at the screening visit, in which participants will consent to all of the study experiments separately. Subjects that withdraw from the study will be replaced. Eligible subjects will be randomized to receive either AMT cream or placebo in a 2:1 allocation ratio (AMT cream: placebo).

Subjects will be instructed to apply either the AMT or vehicle cream to both arms twice a day for seven days. Both subjects and clinical investigators will be blinded. Optional follow-up visits to assess clinical effect and steady state may occur at 1 and 4 hours after initial cream application if the subjects are willing to return at these time points. 4 days after the treatment visit, subjects will return to the clinic for fresh aliquots of the AMT and vehicle creams as well as to assess safety and clinical effect. Subjects will return to clinic after the seven day course of AMT or vehicle creams for clinical and safety assessments. Subjects will then be asked to return to the clinic 1 day after completion of the AMT or vehicle cream course for additional safety and clinical effect assessments. Subsequently, subjects will return for additional follow-up visits only if their lesional atopic dermatitis sites have not yet returned to baseline (*S. aureus* is no longer inhibited and *Staph species* from the AMT cream is zero). Up to 27 subjects will be recruited for this entire study. The duration of this study is approximately 2 months. We anticipate the entire study duration will be approximately 2 years total, and that it will take approximately 1 year to reach recruitment and enrollment goals for this study. The study flow diagram is provided in Figure 1.

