Intervention(s) and comparators: A coded cream consisting of Cetaphil® Moisturizing Lotion alone, or the microbiome transplant consisting of Cetaphil® Moisturizing Lotion plus 10^{5-8} CFU/gram Cetaphil® of coagulase negative *Staphylococci* clones expressing antimicrobial products isolated from the subject's own non-lesional skin. Since the two creams are indistinguishable in terms of color and texture, both the study coordinator and the subject will remain blinded to the identity of the cream. Our goal is to achieve a density of 1

$X 10^5$ CFU/10mg/cm² at the time of application. This abundance is known to be safe as it is the density of bacteria typically found on normal skin.

[Insert a schematic diagram of the trial here (include study cohorts and sample size, treatment allocation, time points of study intervention and subject follow-ups)]

Table format

Cohort	27 subjects	ARM 1	18 subjects: AMT cream
		ARM 2	9 subjects: Vehicle cream only

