4.2. Inclusion Criteria

Up to 54 subjects with atopic dermatitis will be enrolled in this study. Enrollment will not take race or gender into consideration. Pregnant women, children (under age 18), and unhealthy subjects with significant co-morbid conditions as determined by the PI will be excluded.

1. Male or female subjects who are not pregnant or lactating. Female subjects of child-bearing potential must have a negative urine pregnancy test on the day of the screening visit in order to be eligible for the study.
2. 18-60 years of age
3. Diagnosis of atopic dermatitis for at least 6 months using the Hanifin and Rajka Diagnostic Criteria for atopic dermatitis
4. Presence of lesional atopic dermatitis skin in both antecubital fossae
5. Positive *S. aureus* colonization based on results of a skin culture taken from one of their AD-affected antecubital fossae during the screening visit
6. Positive for antimicrobial CoNS species from non-lesional AD skin

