13.1 Overview

We propose here a randomized, double-blind, placebo-controlled trial that will apply beneficial bacteria from the AD host onto lesional skin of AD patients, thus performing an autologous microbiome transplant. Up to 54 subjects with AD will be recruited.

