13.4.2 Primary Analysis of Primary Endpoint(s)/Outcome(s)

Aim: The change in *S. aureus* abundance after 7 days of AMT cream by using skin swabs to determine the quantity of *S. aureus* using culture and qPCR.

For each AD subject, the abundance of *S. aureus* will be calculated using CFU counts from baseline (day 28) to Day 35 after 7 days of AMT cream application or placebo application. Comparisons of *S. aureus* reduction will be made between AMT cream and placebo subjects using a two-tailed t-test for independent samples with type II error rate of 0.2 and type I error rate of 0.05. The sample size will include 18 subjects in the AMT cream arm and 9 subjects in the placebo arm. Comparisons of AMT cream versus placebo cream will be reported as means, standard deviations, medians, and minimum and maximum. An intention-to-treat analysis will be conducted that includes all subjects who had at least one follow-up visit after intervention. A per-protocol analysis will also be conducted that includes all subjects who were compliant with the full intervention regimen with no major protocol violations.

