13.7 Sample Size Considerations

Number of *S. aureus* colonies will be a continuous variable, and change in *S. aureus* abundance will be measured as the absolute difference in number of colony-forming units at specified time points.

The sample size was calculated using G-Power Data Analysis software for a two-tailed t-test for independent samples, type II error rate of 0.2, and type I error rate of 0.05. The values used in the analysis were determined from our pilot study in which we quantified the reduction in *S. aureus* on the forearms of 5 atopic dermatitis patients twenty-four hours after treatment with a live microbiome transplant. Since the sample size was small in this study, we used the median and median average deviation as measures of central tendency. The median *S. aureus* present on the forearms of atopic dermatitis patients at baseline was 192.86 CFU/cm² with deviation of 191.86. We observed that a log-base 10 reduction by 1 of the number of bacteria present on the forearms to be a clinically significant reduction at 24 hours, with deviation of 21.42. Using $\mu_1 = 192.86$, $\mu_2 = 19.186$, and $\sigma_1 = 191.86$, and $\sigma_2 = 21.42$, the total sample size necessary to see this difference would be $n=24$ for an unequal allocation of subjects 2:1 in the treatment to placebo groups.

Assuming a drop-out rate of 20%, we propose a total $n=27$, with $n= 18$ in the treatment group and $n= 9$ in the placebo group. Assignment to treatment or placebo groups will be determined using simple randomization with an online random number generator.

This sample size is reasonable and practical within the scope of this funding mechanism and recruitment capabilities.

An intention-to-treat analysis will be conducted that includes all subjects who had at least one follow-up visit after intervention. A per-protocol analysis will also be conducted that includes all subjects who were compliant with the full intervention regimen with no major protocol violations.

14. Identification and Access to Source Data

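### Simple 2:1 randomisation does not secure the stated 18:9 arms; the cost is a modest lower-tail power risk that a blocked list would remove almost for free

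*Combined protocol and SAP*

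**What the plan says.** **Method of allocation.** Section 3.2 assigns the task to an unblinded laboratory member at a 2:1 ratio: "This unblinded pharmacist will use an online tool to generate a simple randomization list". Section 13.7 says the same: "Assignment to treatment or placebo groups will be determined using simple randomization with an online random number generator". Neither section mentions blocks, strata or fixed arm totals, and nor does any other section.

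**Arm sizes.** Section 13.4.2 states: "The sample size will include 18 subjects in the AMT cream arm and 9 subjects in the placebo arm". The cohort table in 3.1 lists 18 subjects on AMT cream and "9 subjects: Vehicle cream only". Section 13.7 proposes 27 in total, split 18 and 9, in the sentence directly before the one on simple randomisation.

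**List length.** Section 3.1 says "Up to 27 subjects will be recruited for this entire study", whereas 4.2 says "Up to 54 subjects with atopic dermatitis will be enrolled in this study" and 13.1 also gives 54. Section 11.3 replaces participants who withdraw or are withdrawn, but no section says how a replacement is allocated.

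**The concern.** In the usual sense of the term, simple randomisation assigns each subject independently. With a one-third chance of placebo it gives 9 placebo subjects in 27 on average, but it does not guarantee 9. The plan therefore names arm sizes that its stated procedure does not deliver.

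Placebo is the smaller arm, so a chance shortfall there costs more power than an equal shortfall on AMT would. The trial is run once, at whatever split occurs. What is at stake is the power of the primary comparison in an unlucky draw, not its validity.

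**Working it through.** **Inputs, all from 13.7.** Means 192.86 and 19.186 CFU/cm²; SDs 191.86 and 21.42; two-tailed independent-samples t-test; type I error 0.05; type II error 0.2; 2:1 allocation; n = 24 before drop-out and 27 (18:9) after.

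**Step 1: reproduce the plan's n = 24.**

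- Averaged SD = √[(191.86² + 21.42²)/2] = 136.51
- d = (192.86 − 19.186)/136.51 = 173.674/136.51 = 1.272
- Noncentral-t power at 16:8 is 0.802, so 24 is recovered. The power figures in step 3 therefore use the plan's own basis.

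**Step 2: distribution of the placebo count.** Under independent assignment, K ~ Binomial(27, 1/3), with mean 9 and SD √(27 × 1/3 × 2/3) = 2.45.

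| Placebo count | Probability |
|---|---|
| exactly 9 | 16.1% |
| 8 to 10 | 45.9% |
| 7 or fewer | 27.5% |
| 6 or fewer | 15.3% |
| 5 or fewer | 7.2% |
| 12 or more | 15.4% |

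**Step 3: power at each split.** Noncentrality is d·√(n₁n₂/27) on 25 degrees of freedom, with all 27 evaluable.

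| AMT:placebo | Power |
|---|---|
| 22:5 | 0.694 |
| 21:6 | 0.752 |
| 20:7 | 0.795 |
| 19:8 | 0.827 |
| 18:9 | 0.850 |
| 17:10 | 0.866 |
| 15:12 | 0.884 |

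Mean power = Σ P(K = k) × power(27 − k, k) = 0.828. Against 0.850 with the arms fixed at 18:9, the loss is 0.850 − 0.828 = 0.022, about 2 points.

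**Step 4: sensitivity to the averaged SD.** Simulation with normal data and the plan's two SDs kept separate (the larger in placebo) gives:

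- Student t-test: 0.891 at 18:9 and a mean of 0.885 over splits, a loss of about 0.6 points
- Welch: 0.663 at 18:9 and a mean of 0.637, a loss of about 2.6 points

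**Step 5: the alternative reading.** Suppose the list holds exactly 18 and 9 in random order. The split at 27 is then certain and steps 2 and 3 do not apply there. If accrual stopped at 24 (an illustrative figure, not one the plan gives as a stopping point), the placebo count would be hypergeometric: the first 24 of 27 entries, 9 of them placebo. P(exactly 8) = 0.471, so the 2:1 ratio would be met less than half the time.

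**The case against.** The strongest reply is that simple randomisation is valid and the harm is small. It introduces no bias, average power stays above 0.80, and 7 placebo subjects give 0.795, which hardly differs from the 0.80 target. Imbalance can also help: 12 or more placebo subjects is as likely as 6 or fewer, and power at 15:12 exceeds the planned 0.850. All of this stands and is why the point is modest.

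A second reply is that 'simple' may only mean unstratified and unblocked, with list totals fixed at 18 and 9. The repeated 18 and 9 give this some support. However, no section states fixed totals, and 13.7's reference to a random number generator favours the literal reading. Under the fixed-total reading the list length (27 or 54) and the handling of replacements would still be open.

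Two stronger inferences should be resisted. A reader might take the 16.1% chance of exactly 9 as damage in itself. It is not, since power at 8 or 10 placebo subjects is 0.827 or 0.866. A reader might also cite the low Welch power at small placebo counts as the true cost. The plan specifies an independent-samples t-test without naming Welch, and how that test behaves under unequal SDs is a separate question from how subjects are allocated.

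**Conclusion.** The point holds as a cheap improvement. The written procedure does not secure the stated arms. Under independent assignment of 27 subjects there is a 15.3% chance of 6 or fewer on placebo, where power is 0.752 or less on the plan's own calculation. The average cost is about 2 points (0.850 to 0.828).

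This rests on three assumptions: the literal meaning of simple randomisation, exactly 27 randomised with all evaluable, and the averaged SD behind n = 24. With the plan's unequal SDs the mean loss is about 0.6 points for Student and about 2.6 for Welch. If a fixed 18/9 list was intended, the figures lapse at 27, and what remains is possible drift from early stopping or replacements.

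The documents do not support a claim that the trial is biased by its allocation method, or that this choice alone leaves it underpowered on average.

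**What to change.** In 3.2 and 13.7, replace simple randomisation with a concealed permuted-block 2:1 list totalling 27. One option is blocks of 3 and 6 in a random order constrained to that total, for example three of each: 3 × 3 + 3 × 6 = 27. State that the list is generated before first enrolment, that block sizes are withheld from clinical staff, and that it is extended in complete 2:1 blocks for replacements. State also that this secures 18:9 among the first 27 randomised, not among completers.

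If accrual stops early, blocks of 3 and 6 keep the placebo count within 1.33 subjects of one third of those randomised.

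The cost is about one sentence in each section and no extra subjects. The downside is predictability at block ends. If block size and all earlier assignments became known, 44% of assignments would be determined with blocks of 3 and 29% with blocks of 6; simple randomisation has none of this. The double blind and undisclosed, varying block sizes limit it.

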3.2.1. Procedure for Unblinding/Unmasking

In order to minimize potential bias from Investigators, investigational staff, and patients, the study will be conducted in a double-blind manner, except for the unblinded laboratory staff for study drug preparation, who will be the only unblinded study site personnel at the site.

Unblinding will occur in cases of emergency situations requiring the knowledge of a given treatment. As per regulatory reporting requirements, the blind will be broken for all unexpected serious adverse events that are considered by the investigator to be related to the study drug. Details of patients who are unblinded during the study will be included in the Clinical Study Report. The blind will be broken only if specific emergency treatment would be dictated by knowing the treatment status of the patient. Unblinding will be approved by the study Safety Officer unless an immediate life threatening condition has developed and the Safety Officer is not accessible. The site investigator will also notify KAI and NIAMS regarding the emergency unblinding event on the next business day.

A full account of the event will be recorded, including the date and time of the unblinding, the reason for the decision to unblind, and the name of the individual who made the decision and the names of the Medical Monitor and others who were notified. The reasons for unblinding of a participant's treatment will be included in the final study report.

Unblinding the study due to an approved interim analysis, final analysis, or study termination will require written approval from NIAMS.

4. Selection of Participants and Clinical Sites/Laboratories

4.1. Rationale for Study Population

In atopic dermatitis, a state of microbial imbalance known as dysbiosis occurs and is closely associated with disease severity. An important characteristic of the dysbiosis in AD is an increased abundance of *S. aureus* and a decrease in overall bacterial diversity. Several lines of experimental evidence support the concept that the multiple defects in epithelial barrier function in AD promote dysbiosis and that this dysbiosis then promotes the immunological disorder characteristic of AD.

4.2. Inclusion Criteria

Up to 54 subjects with atopic dermatitis will be enrolled in this study. Enrollment will not take race or gender into consideration. Pregnant women, children (under age 18), and unhealthy subjects with significant co-morbid conditions as determined by the PI will be excluded.

1. Male or female subjects who are not pregnant or lactating. Female subjects of child-bearing potential must have a negative urine pregnancy test on the day of the screening visit in order to be eligible for the study.
2. 18-60 years of age
3. Diagnosis of atopic dermatitis for at least 6 months using the Hanifin and Rajka Diagnostic Criteria for atopic dermatitis
4. Presence of lesional atopic dermatitis skin in both antecubital fossae
5. Positive *S. aureus* colonization based on results of a skin culture taken from one of their AD-affected antecubital fossae during the screening visit
6. Positive for antimicrobial CoNS species from non-lesional AD skin

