8.1. Enrollment

The research study will be explained in lay terms to each potential research participant. The potential participant will sign an informed consent form before undergoing any study procedures. Once the informed consent has been signed, and meets all the inclusion and exclusion criteria, the participant is considered enrolled in the study and will be assigned a unique participant number.

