8.3. Study Visits or Study Assessments

Aim: To determine the change in abundance of *Staph aureus* from baseline after 1 week BID application of AMT.

The study flowchart is provided below:

This experiment will consist of up to 9 office visits (Screening, Treatment, 2 optional visits, and 5 Follow-up visits) and two phone calls. All office visits will occur at the UCSD Dermatology Clinic. Up to twenty seven (27) subjects with AD will be recruited for this study. The exact study procedures are noted below:

Screening Visit 1 (Day -60 to Day -2)

Prior to beginning any study procedures, subjects will first be asked to review and sign the informed consent form. After obtaining informed consent, the inclusion/exclusion criteria will be reviewed. A brief medical history, vital signs, and physical exam will be performed in helping to assess whether the subject meets the required criteria for the study. Female subjects of child-bearing potential will complete a urine pregnancy test while in our office to ensure that they are not pregnant. Patients who meet the inclusion and exclusion criteria

will then have their lesional AD skin scored according to the SCORAD grading scale, EASI, and modified EASI, and localized SCORAD, and the extent of AD lesional skin on their bilateral arms will be recorded. A skin swab will be performed on the lesional atopic dermatitis skin of their antecubital fossae bilaterally to detect the presence of *S. aureus*. Additionally, we will take four (4) culture swabs from the subject's non-lesional (no AD) skin on their upper arms. These culture swabs will be placed in tryptic soy broth (TSB) until processed in the lab, where they will be used to grow the subject's antimicrobial peptide-producing *Staph* species to use for the autologous microbiome transplant. Subjects will then receive a bar of Dove moisturizing soap, which they will be instructed to use whenever they shower until after the follow-up visit is complete. This will conclude the screening visit. The total time for this visit will be approximately 40 minutes.

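### Sections 4.2 and 13.1 plan for up to 54 subjects; the synopsis and every section that gives arm sizes or a rationale plan for 27

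*Combined protocol and SAP*

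**What the plan says.** Two sections give 54. Section 4.2 opens with "Up to 54 subjects with atopic dermatitis will be enrolled in this study". Section 13.1, the overview of the statistical section, has "Up to 54 subjects with AD will be recruited".

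The rest of the document gives 27:

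- The synopsis sets an accrual objective of 27.
- Section 3.1: "Up to 27 subjects will be recruited for this entire study".
- The design table in 3.1 shows one cohort with two arms, "18 subjects: AMT cream" and "9 subjects: Vehicle cream only".
- Section 8.3: "Up to twenty seven (27) subjects with AD will be recruited for this study".
- Section 13.4.2: "The sample size will include 18 subjects in the AMT cream arm and 9 subjects in the placebo arm".
- Section 13.7 derives a total of 24, then proposes 27 after an allowance for drop-out.

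Two further provisions bear on how these figures are read. Section 8.1 says that once a person has consented and satisfies the eligibility criteria, "the participant is considered enrolled in the study and will be assigned a unique participant number". Sections 3.1 and 11.3 replace subjects who withdraw and give no upper limit on replacements.

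**The concern.** The planned number of subjects fixes how many people may be exposed to a live-bacteria product, when recruitment ends and which data set is analysed. Here the statistical section disagrees with itself (13.1 against 13.4.2 and 13.7), and the eligibility section disagrees with the design section. Section 15.1 treats any departure from the design as a deviation, yet the text cannot settle whether a 28th subject, not brought in as a replacement, is one.

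There is a possible knock-on effect. Two of the three halting triggers in section 11.5, repeated in 12.8.2.2 and 12.8.2.2.1, are set at 10% of the study population. If that term means the planned total, the ambiguity carries into the number of affected subjects that halts the trial.

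**Working it through.** **1. What stands behind 27.** Inputs from section 13.7: means 192.86 and 19.186, deviations 191.86 and 21.42, two-sided type I error 0.05, type II error 0.2, allocation 2:1. The section states no standardised effect. I assume the equal-weight average of the two variances:

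- difference = 192.86 − 19.186 = 173.674
- SD = √[(191.86² + 21.42²)/2] = 136.51
- d = 173.674/136.51 = 1.272

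The noncentral t distribution gives power 0.802 at 16 + 8, so the plan's total of 24 is reproduced. The step from 24 to 27 is looser than stated, because 24/(1 − 0.2) = 30 and 27 corresponds to drop-out of 1 − 24/27 = 11%. That is a separate matter. Here it is enough that 27 has a stated route and fixed arms (18 + 9 = 27).

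**2. Can 54 be reached by any route in the documents?**

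- *Sample-size formula.* One-sided testing, 1:1 allocation, other ways of combining the two deviations and an unequal-variance formula were tried. None gives 54, which is exactly 2 × 27.
- *Drop-out.* 24/0.8 = 30, not 54.
- *Replacements.* Going from 27 to 54 takes 27 replacements, one for every planned subject. At the assumed 20% drop-out, keeping 27 completers needs 27/0.8 = 33.75, or 34 subjects.
- *A second cohort.* Section 3.1 applies its 27 to the entire study, and the design table has one cohort.
- *A screening ceiling.* Section 4.2 says enrolled, which 8.1 defines as consented and eligible. Section 8.3 enrols subjects only after positive screening cultures. Section 13.4.6 tabulates enrolled subjects by randomised group. Section 13.4.1 has a separate term, Screening Population, for everyone who consents.
- *Different verbs.* Sections 3.1, 8.3 and 13.1 all say recruited, with 27, 27 and 54.

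No route leads to 54.

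**3. The halting triggers, if the denominator is the planned total.** The count is 10% of N, rounded up.

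| Planned N | 10% of N | Subjects to trigger | Share |
|---|---|---|---|
| 27 | 2.7 | 3 | 3/27 = 11.1% |
| 54 | 5.4 | 6 | 6/54 = 11.1% |

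Three affected subjects would meet the trigger at 27 but be only 3/54 = 5.6% at 54. The remaining trigger, a single serious event reasonably possibly caused by the product, does not depend on N.

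**The case against.** The strongest reply is that 27 is plainly the working figure. It is the accrual objective, it alone is split into arms, it is the size used in the primary analysis, and it alone has a derivation. Both figures are also worded as maxima, so a trial that stops at 27 satisfies every section. That stands, and it limits the point to a correction of two sentences.

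It also stands that enrolled is not the same as randomised. Between enrolment and randomisation at Visit 3, medication use is rechecked and the arms are examined, and a bacterial stock that fails contaminant testing is discarded (6.1.1.1). Section 4.2 alone therefore does not say that 54 will be randomised. This does not rescue 13.1, which uses the same verb as 3.1 and 8.3 with a different number. Nor is 54 the only opening for recruitment past 27, since replacements have no stated limit.

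Stronger readings are tempting but unsupported:

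- A reader might infer that the trial has no fixed size. The arm sizes and section 13.7 say otherwise.
- A reader might infer two competing designs, 18 + 9 and 36 + 18, with different power. No section randomises or analyses 54, and a larger trial would not lose power.
- A reader might infer that the halting rule has two thresholds as a matter of fact. The term study population is never defined. It could mean planned, randomised or treated to date, and on the last reading the count changes as the trial proceeds, whichever total is planned.

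**Conclusion.** The inconsistency is real and unexplained in the current text: 54 in sections 4.2 and 13.1, and 27 in the synopsis, 3.1 with its design table, 8.3, 13.4.2 and 13.7. The gap is a factor of two. The direct consequence is that a 28th subject who is not a replacement is allowed by two sections and excluded by others. It is an internal inconsistency, not a calculation error, and it does not undermine the primary comparison. It should still be corrected, because sample size is a figure the trial relies on.

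The effect on halting (3 subjects or 6) is secondary. It rests wholly on the assumption that the denominator is the planned total, which the documents do not say, so correcting 54 alone would not settle that threshold. The figure 54 may be left over from other text, but nothing in the documents shows this.

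**What to change.** In sections 4.2 and 13.1, replace 54 with: *up to 27 randomised (18 AMT, 9 vehicle), plus replacements for withdrawals*. If 54 was meant as a limit on screening, write *up to 54 screened* there and keep 27 as the number randomised.

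In the same amendment, reconcile sections 11.5, 12.8.2.2 and 12.8.2.2.1 with the corrected total by stating what study population means in the 10% triggers. The choice of denominator is for the sponsor and its safety advisers.

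The cost is two wording changes for the sample size and one definition for the halting rules. No recalculation and no change to procedures or analysis are needed.
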